3.1 Study Design

3.1.1 Description

This is a randomized, double-blind, parallel group, multicenter, Phase 3 transition study in subjects with active RA who are eligible for the subsequent treatment course with US-rituximab or EU-rituximab according to the clinical judgment of the investigator.

It is planned to randomize 140 subjects (70 per treatment arm) at approximately 50 sites in up to 7 countries (including, but not restricted to the United States).

A course of treatment with US-rituximab or EU-rituximab in RA consists of two 1000 mg IV infusions separated by 2 weeks. Subjects with RA who have received at least 1 full course comprising two 1000 mg infusions with either US-rituximab or EU-rituximab will be eligible for the study. The rituximab reference product (US-licensed rituximab [Rituxan] or EU-approved rituximab [Mabthera]) used should be the same in the prior and the randomized treatment course, respectively. Subjects having received the prior treatment course with reference products other than US-licensed rituximab (Rituxan) or EU-approved rituximab (Mabthera) will not be eligible for the study. Subjects should not be switched from the prior to the randomized treatment course from US-licensed to EU-approved reference product or vice versa.

Subjects will then be randomized by interactive web response system (IWRS) to receive either two 1000 mg infusions of DRL_RI (Arm A) or US-rituximab/EU-rituximab (Arm B) on Day 1 and Day 15. This will constitute the next course of rituximab treatment. Subjects randomized to Arm A will receive DRL_RI and subjects randomized to Arm B will continue to receive either US-rituximab or EU-rituximab.

The study will consist of a screening period (Days -14 to 0) and a double-blind period (Day 1 to Week 12). Subjects will attend a screening visit followed by visits at Weeks 0 (Day 1), 2, 4, 8, and 12 (end of study [EOS]) after randomization. An additional follow-up visit will be conducted at Week 26 to evaluate safety and to perform a serum pregnancy test in women of childbearing potential (WOCBP).

[figure not shown]
Subjects having signed the informed consent form (ICF) versions prior to the one introduced by this amendment need to re-consent to continue participating in the study after Week 12 through Week 26. If a subject does not re-consent for further study participation after Week 12, then his/her study data up to Week 12 will be collected and the subject will be discontinued from the study.

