3.1.4 End of Study

End of study is defined as the time at which all subjects enrolled in the study have been followed for 10 weeks after treatment unless lost to follow-up or the subject has died. The EOS is achieved at the last subject's Week 12 visit. After EOS, an additional follow-up visit will be conducted at Week 26 to evaluate safety and to perform a serum pregnancy test in WOCBP.

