4.2 Withdrawal of Subjects From Study Treatment and/or the Study

The duration of the study is defined for each subject as the date when signed written ICF is provided through the EOS visit on Week 12. An additional follow-up visit will be conducted at Week 26 to evaluate safety and to perform a serum pregnancy test in WOCBP. Subjects having signed the ICF versions prior to the one introduced by this amendment need to re-consent to continue participating in the study after Week 12 through Week 26. If a subject does not re-consent for further study participation after Week 12, then his/her study data up to Week 12 will be collected and the subject will be discontinued from the study.

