5.7 Blinding

A double-blind design is employed so that both the investigators and the subjects will be unaware of the treatment assignment during the whole study. Moreover, study center staff involved in study treatment administration and study endpoints assessments, CRO personnel, and the sponsor team including study statistician will be blinded to the treatment received. The clinical laboratories analyzing the blood/plasma samples and the concentration/incidence of anti-rituximab antibodies will also be blinded to the treatment assignment. A team from the CRO, independent to the clinical monitoring group, shall be responsible for maintaining drug accountability logs. An unblinded study coordinator or pharmacist at each site will be responsible for maintaining drug accountability as well as for dispensing. The final CSR will include all end points, after all subjects complete the Week 12 (EOS/ET) visit and the database up to the Week 12 (EOS/ET visit) has been locked. The study will be unblinded after the database up to the EOS/ET visit has been locked. The subsequent follow-up data from Week 12

to 26 will be reported as an addendum to the final CSR and for the data up to and including the Week 12 or ET visit.

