5.7.1 Breaking the Blind

A subject's treatment assignment will not be broken until the EOS unless medical treatment of the subject depends on knowing the study treatment the subject received. In the event that the blind needs to be broken because of a medical emergency, the investigator may unblind an individual subject's treatment allocation.

The study site investigator and appropriate project team members will be authorized to access the emergency unblinding functionality within the IWRS. The system will require the user to enter an authorization key number to complete the emergency unblinding transaction. The exact description of the treatment assigned to the individual subject then will be accessible. Emergency unblinding can thus be made for any subject without affecting the double-blind nature of the study. Subject treatment information may only be accessed in the event of an emergency and out of necessity to know the identity of the allocated study treatment in order to institute appropriate therapeutic management. Should a situation arise where unblinding is urgently required (i.e., knowledge of treatment code is required to adequately manage a life-threatening situation), the investigator at that study site may perform immediate unblinding through the IWRS. If time allows, the investigator should contact the medical monitor prior to unblinding the individual subject to discuss the rationale for emergency unblinding.

In the event that emergency unblinding is performed, the investigator can view and must print the blinded confirmation document from IWRS. The investigator must record on the confirmation document printout the reason for the emergency unblinding and sign the document. The confirmation document must then be kept in a safe place until Week 26. Once a randomization code has been broken for a subject, he/she must be withdrawn from the study. The investigator must inform the medical monitor/designee in writing within 24 hours.

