6.3.1.2 Recording of Adverse Events

Any relevant observations made at the screening visit (prior to signing the ICF) are to be recorded as a preexisting condition. For the purposes of this study, any detrimental change in the subject's condition, after signing the ICF and up to completion of the 26-week study period, should be considered as a TEAE/SAE.

The following variables will be recorded for each AE: verbatim/AE description and date for AE start and stop, severity, seriousness, causality rating, whether or not the AE caused the subject to discontinue, action taken with the study treatment, and the outcome. If the severity of the event changes, the event with the highest severity will be recorded.

Serious AEs and TEAEs will be recorded starting after signing of the ICF. All SAEs and AEs have to be recorded, whether or not considered causally related to the study treatment or to the study procedure(s).

All ongoing nonserious AEs should be followed up until resolution or stabilization or the EOS/ET visit, whichever occurs first, with the exception of any ongoing treatment-related nonserious AEs that should be followed until that AE is stabilized, resolved, or, in the investigator's opinion, the AE is unlikely to resolve due to the subject's underlying condition.

All ongoing SAEs should be followed up until resolution or stabilization/or until a pre-defined outcome is reached.

Note: Outcome information received on on-going SAE beyond the date of data base lock, will be captured in safety database and reported as follow-up report in the form of individual case safety report.

At any time after the additional follow-up visit, if an investigator learns of an SAE that can be reasonably related to study treatment, he/she should promptly notify the sponsor/designee.

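### Protocol 5.7 unblinds the study at the Week 12 lock without limiting who receives the codes, while subjects may still be in adverse-event follow-up to Week 26

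*Protocol*

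**What the plan says.** **Unblinding.** Protocol 5.7 says "The study will be unblinded after the database up to the EOS/ET visit has been locked". It names neither the recipients of the codes nor anyone who stays blinded afterwards. The same section says that "both the investigators and the subjects will be unaware of the treatment assignment during the whole study", and it lists site assessors, CRO personnel and the sponsor team as blinded without giving an end date.

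**Length of the blind.** Protocol 3.1.1 describes "a double-blind period (Day 1 to Week 12"), and SAP 3.1 gives the same period. Protocol 5.7.1 says that a subject's "treatment assignment will not be broken until the EOS", with an exception for medical need; Protocol 3.1.4 sets EOS at the last subject's Week 12 visit. Protocol 5.7.1 also says "Subject treatment information may only be accessed in the event of an emergency".

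**Follow-up.** Protocol 3.1.4 adds: "After EOS, an additional follow-up visit will be conducted at Week 26 to evaluate safety". AEs are assessed at that visit (Protocol 6.1.5). Under Protocol 6.3.1.2, any detrimental change "after signing the ICF and up to completion of the 26-week study period, should be considered as a TEAE/SAE". The investigator rates causality and may revise the rating, and the sponsor/CRO separately evaluates each serious AE (Protocol 6.3.1.4).

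**Reporting.** Protocol 3.1.1, 5.7 and 11.4 plan a final report on data to Week 12, with Weeks 12–26 in an addendum. SAP 4.2 puts the Week 12–26 data in the final study report and does not mention the Week 12 unblinding. SAP 10.1 declares one change from the protocol, the added estimand.

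**The concern.** Locking and reporting at Week 12 is a stated design choice, and Amendment 2 explains it (Protocol 14.3.2.1): the data for the primary objective are complete by then. That explains early reporting. It does not require that people who still report or judge AEs should have the codes.

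The gap matters because the study is a descriptive safety comparison with no test or model behind it. Eliciting an AE, grading it and attributing it to the drug all involve judgement, and someone who knows that a subject was switched to the biosimilar may judge differently. If codes circulate beyond the reporting team while subjects are in follow-up, the Week 12–26 data carry a source of bias that a sentence in the protocol could have prevented.

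**Working it through.** There is no stated figure to reproduce. The check is textual, followed by an illustration of size.

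**1. When does the blind end?**

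| Points to Week 12 | Points to Week 26 |
|---|---|
| 5.7: general unblinding after the EOS/ET lock | 5.7: investigators and subjects blinded for the whole study |
| 3.1.1 and SAP 3.1: double-blind period ends at Week 12 | 6.3.1.2: AE recording refers to a 26-week study period |
| 5.7.1 with 3.1.4: codes protected until the last Week 12 visit | 5.7.1: treatment information for emergencies only; emergency confirmation document kept safe to Week 26 |
| 4.2: study duration "defined for each subject as the date when signed written ICF is provided through the EOS visit on Week 12" | Synopsis: participation of about 28 weeks; 4.2 itself adds the Week 26 visit and re-consent to it |

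No passage reconciles the two columns. Protocol 5.7.1 also requires a subject whose code has been broken to leave the study. Applied literally to a study-wide release, that would remove every subject still in follow-up and defeat the planned addendum, so the rule needs to be reconciled with the release in 5.7.

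**2. Which judgements can still be open after the lock?** For subjects between Week 12 and Week 26:
- AE reporting at the site (6.1.5, 6.3.1.2).
- Sponsor/CRO evaluation of serious AEs (6.3.1.4).
- The investigator's causality rating (6.3.1.4). This is the only assessment that SAP 9.1.2 names for the drug-related tables.

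ADA sampling ends at Week 12, both infusions are given by Day 15, and the Week 12 data are locked before the codes are opened. None of these is exposed.

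**3. How many subjects?** The documents give N = 140 (Protocol 3.1.1) and an interval of 26 − 12 = 14 weeks. They give neither the accrual period *A* nor the lag *L* from the last Week 12 visit to the lock. The illustration assumes uniform accrual, nominal visit dates and everyone followed to Week 26. Both formulas are zero when *L* ≥ 14:
- Subjects still in follow-up at the lock = 140 × (14 − L) / A
- Share of all Week 12–26 follow-up time after the lock = (14 − L)² / (2 × A × 14)

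Example, A = 52 and L = 8: 140 × 6 / 52 = 16.2 subjects; 36 / 1456 = 2.5%.

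| Assumed accrual (weeks) | L = 4 | L = 8 | L = 12 | L = 14 |
|---|---|---|---|---|
| 26 | 53.8 (13.7%) | 32.3 (4.9%) | 10.8 (0.5%) | 0 |
| 52 | 26.9 (6.9%) | 16.2 (2.5%) | 5.4 (0.3%) | 0 |
| 78 | 17.9 (4.6%) | 10.8 (1.6%) | 3.6 (0.2%) | 0 |
| 104 | 13.5 (3.4%) | 8.1 (1.2%) | 2.7 (0.1%) | 0 |

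A lag of 0 is left out because the last samples still need tiered ADA/NAb testing (Protocol 6.2.2). Subjects who do not re-consent after Week 12 would lower the counts.

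**4. Report plan.** SAP section 1 says that it is based on Protocol version 3.0, the version that sets the addendum plan. SAP 4.2 still differs from Protocol 3.1.1, 5.7 and 11.4, and SAP 10.1 does not say so. The table titles in SAP 12.2 do not show which AE tables stop at Week 12.

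**The case against.** The strongest reply is that the sensible reading of Protocol 5.7 is unblinding of the analysis team alone. The whole-study blind, the withdrawal rule after a code break and the Week 26 retention rule all favour investigators staying blinded, and no passage says that they will be given the codes. A reader might infer that the plan opens the codes to investigators at Week 12; the documents do not support that. What stands is that 5.7 announces a general unblinding without a limit, while 3.1.1 and 5.7.1 protect the blind only to Week 12.

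A second reply concerns the route to the tables. Sponsor/CRO causality review covers serious AE reports, whereas SAP 9.1.2 names only the investigator's rating. Bias in the drug-related tables would therefore require investigators to know the codes, or some indirect influence on them. This is correct and limits the weight of the point.

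A reader might also infer that causality ratings could distort the primary safety endpoints. They could not do so directly: those endpoints are the incidence of treatment-emergent AEs, serious AEs and reactions, and events are recorded whether or not they are thought related. Only the reporting of late events bears on that incidence.

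Finally, a code-access list may exist in the randomization plan or in study procedures that are not public, and table shells may define the Week 12 cut. Silence in the two documents does not show that controls are absent. It shows that the governing text does not require them.

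**Conclusion.** The point holds as a cheap improvement to consider. Protocol 5.7 sets a general unblinding at the Week 12 lock without limiting recipients, and the protocol conflicts on whether the blind runs to Week 12 or Week 26. The possible effect is limited to Week 12–26 AE reporting and drug-related summaries, in subjects still in follow-up at the lock.

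The size is unknown and may be zero. The largest entry in the illustration, about 54 of 140 subjects, is its extreme corner (26-week accrual, 4-week lag) and should not be read as an estimate. Every entry rests on assumed accrual and lag. The documents show an avoidable opening for bias; they do not show that bias will occur.

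The difference between SAP 4.2 and the protocol is real but secondary. It concerns how the data are packaged and which data cut the AE tables use, and it changes no endpoint, population or method.

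**What to change.** **Protocol 5.7.** State that codes are released at the Week 12 lock only to the team preparing the Week 12 report. Keep investigators, assessing site staff, subjects and AE/SAE reviewers blinded until the Week 26 lock. Leave emergency unblinding (5.7.1) and SUSAR unblinding (6.3.1.5) as they are.

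**Reconcile with this.** Protocol 4.2 (study duration), 5.7.1 (protection until EOS, and withdrawal after a code break) and 6.3.1.2 (26-week study period).

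**SAP.** Align 4.2 with Protocol 3.1.1, 5.7 and 11.4 and say which AE tables are cut at Week 12, or declare the change in SAP 10.1.

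**Cost.** Wording in two documents and an access list. The Week 12 report is not delayed. The downside is that wider sponsor access to the codes waits until the Week 26 lock.

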5.7.1 Breaking the Blind

A subject's treatment assignment will not be broken until the EOS unless medical treatment of the subject depends on knowing the study treatment the subject received. In the event that the blind needs to be broken because of a medical emergency, the investigator may unblind an individual subject's treatment allocation.

The study site investigator and appropriate project team members will be authorized to access the emergency unblinding functionality within the IWRS. The system will require the user to enter an authorization key number to complete the emergency unblinding transaction. The exact description of the treatment assigned to the individual subject then will be accessible. Emergency unblinding can thus be made for any subject without affecting the double-blind nature of the study. Subject treatment information may only be accessed in the event of an emergency and out of necessity to know the identity of the allocated study treatment in order to institute appropriate therapeutic management. Should a situation arise where unblinding is urgently required (i.e., knowledge of treatment code is required to adequately manage a life-threatening situation), the investigator at that study site may perform immediate unblinding through the IWRS. If time allows, the investigator should contact the medical monitor prior to unblinding the individual subject to discuss the rationale for emergency unblinding.

In the event that emergency unblinding is performed, the investigator can view and must print the blinded confirmation document from IWRS. The investigator must record on the confirmation document printout the reason for the emergency unblinding and sign the document. The confirmation document must then be kept in a safe place until Week 26. Once a randomization code has been broken for a subject, he/she must be withdrawn from the study. The investigator must inform the medical monitor/designee in writing within 24 hours.

5.8 Treatment Compliance

Study treatment will be administered under the supervision of the investigator and site personnel. Compliance will be monitored by study personnel at the site by using the source documents and the eCRF. The site study unblinded pharmacist/authorized designee is responsible for drug preparation, the maintenance of accurate and complete dispensing and

accountability forms showing the receipt and dispensation of the study treatment. The pharmacist will also be responsible for performing accountability and reconciliation of the study treatments.

5.9 Prior and Concomitant Therapy

Medications that are considered necessary for the subject's safety and well-being may be given during the course of the study at the discretion of the investigator and must be recorded in the appropriate sections of the eCRF.

All medications taken by a subject within 1 month prior to the screening visit are regarded as **prior medication** and must be documented as such in the eCRF.

All medications still being taken by a subject at randomization and which continue to be taken during the study and medications started during the study are regarded as **concomitant medication** and must be documented as such in the eCRF.

5.9.1 Background Medication

A stable dose of weekly MTX (7.5 mg to 25 mg) and folic acid (at least 5 mg per week) that the subject is receiving are considered as background medications. Subjects have to be on a stable dose of weekly MTX (between 7.5 mg and 25 mg) for at least 4 weeks prior to randomization and during the study and folic acid (at least 5 mg per week).

Note: MTX and folic acid should be used in accordance with the guidelines specified in the local label (e.g., SmPC in the EU, US PI for the US). Folinic acid at the same dose of folic acid, can be given in place of folic acid if it is allowed by the local label. Subject should take the same folate supplementation throughout the duration of the study.

5.9.2 Other Concomitant Medication

Low-dose corticosteroids (≤ 10 mg/day prednisone equivalent) and non-steroidal anti-inflammatory drugs as needed are permitted concomitant medications for RA during this study.

Concomitant administration of any other experimental drug, biological medicinal products, B-cell modulating or cell-depleting biologic therapy, JAK inhibitors, anti-rheumatic drugs including DMARDs other than MTX (along with folic acid), tofacitinib, glucocorticoids used

[name] S.A.

DRL_RI

Protocol: Version 3.0 Amendment 2

10 Jul 2020

as pre-medication other than methylprednisolone or its equivalent, or immunotherapy is prohibited during study participation.

6 Study Assessments and Procedures

Before performing any study procedures, all potential subjects will sign an ICF. Subjects will have the opportunity to have any questions answered before signing the ICF. The investigator must address all questions raised by the subject. The investigator or designee will also sign the ICF.

6.1 Schedule of Assessments

An overview of the protocol visits and procedures is provided in [Table 14-1](#).

The investigator may plan unscheduled visits in addition to those listed on the schedule of activities, in order to conduct evaluations or assessments required to protect the well-being of the subject. If any unscheduled visits happen at any time during the study, visit details/appropriate data including the reason will be collected in the eCRF.

6.1.1 Screening Period (Days -14 to 0)

Subjects will undergo a screening visit, within 14 days prior to the planned first day of study treatment. During the screening visit, subjects will be screened at the study site to confirm their eligibility for participation in the study. The investigator or sub-investigator will discuss with each subject the nature of the study, its requirements, and its restrictions. Written and signed ICF must be obtained from each subject prior to the conduct of any protocol-specific procedures.

Screening procedures and assessments will be as follows:

The proposed chronological order of the assessments below should be followed.

1. Obtain written informed consent from the subject in accordance with local regulations.
2. Register screening of the subject.
3. Review subject eligibility (inclusion and exclusion criteria). Any questions regarding subject eligibility can be addressed to the medical monitor.

4. Document medical and surgical history (includes full history of RA and other rheumatic diseases, including their related procedures, all ongoing conditions at the time of screening, all major surgical procedures [i.e., those involving opening of cavities or epidural or general anesthesia] with their reason, and any past event or procedure considered relevant by the investigator as well as any minor event occurring in the month prior to screening).
5. Document subject demographics.
6. Clinical assessments will include the following: physical examination (including height and weight), vital signs measurement (seated BP, heart rate, respiration rate, and oral body temperature).
7. Serum pregnancy test (beta-human chorionic gonadotropin [β -hCG]) to be performed for WOCBP. Female subjects with documented history of hysterectomy, bilateral salpingectomy, bilateral oophorectomy, medically confirmed ovarian failure, or screening follicle-stimulating hormone (FSH) test demonstrating postmenopausal status are exempted from pregnancy testing.
8. Clinical laboratory assessments: a blood sample will be taken for hematology and biochemistry; urinalysis will also be performed.
9. Tuberculosis screening (if required by local regulation or practice).
10. Viral disease screening: hepatitis B surface antigen (HBsAg), hepatitis B core antibody (HBcAb), hepatitis C virus (HCV), and human immunodeficiency virus (HIV).
Note: For HBcAb, site is requested to perform HBcAb IgG and HBcAb IgM. If any of these 2 results is positive, then the subject will be considered as screen failure.
11. Twelve-lead electrocardiogram (ECG).
12. Assess AE(s).
13. Prior and ongoing medications.
14. Serum Immunoglobulin (IgG and IgM)

Subjects who do not meet the criteria for participation in this study (screen failure) may be rescreened at the investigator's discretion, following discussion with the sponsor designee medical monitor. Subjects not included in the study due to latent TB (in the locations where

TB screening is required) will also require rescreening after appropriate treatment has been administered per local guidance.

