- Abnormal liver function tests such as aspartate aminotransferase, alanine aminotransferase, or alkaline phosphatase $>2 \times$ upper limit of normal (ULN). A single parameter $>2 \times$ ULN can be re-checked as soon as possible, at least prior to randomization, if required as per the investigator's discretion.
- Creatinine clearance (Cockcroft & Gault formula) of less than 50 mL/min.

14. History of vaccination with live vaccines within 4 weeks of the first dose of study treatment (Day 1) or known to require live vaccines during the study.

15. Lactating or pregnant female.

16. Women of childbearing potential who do not consent to use highly effective methods of birth control during treatment and for at least 12 months after the last administration of study treatment.

Note: Per the Clinical Trial Facilitation Group (CTFG) guidelines 2014, a woman is considered of childbearing potential if fertile, following menarche until becoming postmenopausal (i.e., no menses for 12 months without an alternative medical cause) unless permanently sterile through hysterectomy, bilateral salpingectomy, and bilateral oophorectomy). Highly effective birth control measures per CTFG guidelines 2014 include the following:

- combined (estrogen and progestogen containing) hormonal contraception associated with inhibition of ovulation - oral, intravaginal, and transdermal
- progestogen-only hormonal contraception associated with inhibition of ovulation - oral, injectable, and implantable
- intrauterine device
- intrauterine hormone-releasing system
- bilateral tubal occlusion
- vasectomised partner
- sexual abstinence

Site should advise subjects to use any of the methods listed above, or per the country/site-specific requirements.

17. Sexually active male subjects unless permanently sterile by bilateral orchidectomy, who do not agree to use 1 of the highly effective methods of birth control listed in Exclusion Criterion #16 during treatment and for at least 12 months after the last administration of study treatment.
18. Subjects with serum IgG <LLN.

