6.1.4 End of Study/Early Termination Visit (Week 12 ± 7 Days)

Subjects who complete the study or discontinue from the study at any time will attend an EOS/ET visit.

The EOS/ET assessments are as follows:

1. Clinical assessments will include the following: physical examination (including weight), vital signs measurement (seated BP, heart rate, respiration rate, and oral body temperature).
2. Serum pregnancy test (β -hCG) for WOCBP. Female subjects with documented history of hysterectomy, bilateral salpingectomy, bilateral oophorectomy, medically confirmed ovarian failure, or screening FSH test demonstrating postmenopausal status are exempted from pregnancy testing.
3. Clinical laboratory assessments: a blood sample will be taken for hematology and biochemistry; urinalysis will also be performed.
4. Twelve-lead ECG.
5. Collect plasma samples for immunogenicity assessments.
6. Collect a time-matched blood sample (approximately 5 mL) for the estimation of rituximab concentration.
7. Assess AE(s).
8. Review concomitant medication(s).

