6.3.4 Clinical Laboratory Assessments

Clinical laboratory assessments will be performed as indicated in [Table 14-1](#). Hematology, biochemistry, and urinalysis will be conducted at the following visits: screening, on Day 1, Day 15, and at Weeks 4, 8, 12 (EOS/ET), and 26 (additional follow-up). Serum pregnancy test will be conducted at screening, Week 12 (EOS/ET), and Week 26 (additional follow-up) visits. Urine pregnancy test will be conducted on Day 1 prior to randomization, and Day 15 (before dosing), at Week 4 and Week 8 visits.

Hematology, biochemistry, urinalysis, and pregnancy tests will be performed by the local laboratory according to local practice. Local laboratory normal ranges will be collected prior to first subject first visit at each site and provided to data management via the study team. Laboratory results collected from the local laboratory should be entered in the eCRF by the investigator. The following parameters will be assessed:

- Hematology: red blood cell count, white blood cell count with differential count and percentages (including absolute neutrophil count), total hemoglobin, hematocrit, platelet count, and prothrombin time.
- Biochemistry: creatinine, blood urea nitrogen, fasting serum glucose, aspartate aminotransferase, alanine aminotransferase, gamma-glutamyl transpeptidase, total bilirubin, albumin, chloride, calcium, phosphorous, uric acid, total protein, sodium, and potassium.
- Serum IgG and IgM.
- Urinalysis (specific gravity, pH, protein, glucose, and blood).
- Pregnancy test: serum β -hCG test and urine pregnancy test for WOCBP.
- Serum FSH for postmenopausal women.

Note: Per CTFG 2014 guidelines, a postmenopausal state is defined as no menses for 12 months without an alternative medical cause. A high FSH level in postmenopausal women is to be used to confirm a postmenopausal state in women not using hormonal contraception or hormonal replacement therapy. However, in the absence of 12 months of amenorrhea, a single FSH measurement is insufficient. Hence, in such cases or in some other cases in which if menopausal status is difficult to confirm, then investigators are advised to investigate further to rule out childbearing potential along with serum FSH.

Blood and urine collection and blood sample preparation will be performed according to procedures from the local laboratories.

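### The FSH exemption from pregnancy testing in protocol sections 6.1.1, 6.1.4 and 6.1.5 conflicts with section 6.3.4 and exclusion criterion 16, and its reach over the urine tests is not stated

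*Protocol*

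**What the plan says.** Three parts of the protocol bear on whether a woman is tested for pregnancy.

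- **Visit sections with a serum test (6.1.1 step 7, 6.1.4 item 2, 6.1.5 item 2).** Each asks for a serum test in women of childbearing potential and then lists grounds for exemption, joined by *or*: any of three operations, confirmed ovarian failure, or FSH. The last ground in section 6.1.1 reads "screening follicle-stimulating hormone (FSH) test demonstrating postmenopausal status are exempted from pregnancy testing". Section 6.1.4 has "screening FSH test demonstrating postmenopausal status are exempted from pregnancy testing", and section 6.1.5 uses the same words.
- **Section 6.3.4.** Its note defines the postmenopausal state by 12 months without menses and uses a high FSH to confirm it. It then warns: "However, in the absence of 12 months of amenorrhea, a single FSH measurement is insufficient". In such cases, or where status is otherwise hard to confirm, "investigators are advised to investigate further to rule out childbearing potential along with serum FSH".
- **Exclusion criterion 16 (section 4.1.2 and synopsis).** A woman is of childbearing potential "following menarche until becoming postmenopausal (i.e., no menses for 12 months without an alternative medical cause"), unless permanently sterile. Neither FSH nor ovarian failure appears in this definition.

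On scheduling, section 6.3.4 states: "Serum pregnancy test will be conducted at screening, Week 12 (EOS/ET), and Week 26 (additional follow-up) visits". It places urine tests on Day 1, Day 15, Week 4 and Week 8. The urine steps in sections 6.1.2 and 6.1.3, and footnote h of Table 14-1, apply to women of childbearing potential and carry no FSH exemption.

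**The concern.** The same woman can be classified differently depending on which section a site follows. A site working from the screening checklist can exempt a woman on her FSH result alone. A site working from criterion 16 or section 6.3.4 would keep her in the tested group. Each site could cite protocol text, so the difference would be hard to detect in monitoring across some 50 sites in up to 7 countries.

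Participant protection is at stake; the immunogenicity endpoint is not. Criterion 15 excludes pregnant women, section 6.4 stops further study treatment once a pregnancy is reported, and the scheduled tests are the planned objective check for both. The overview of Amendment 2 (section 14.3.2.1) gives monitoring of contraception in women of childbearing potential as one reason for the Week 26 visit. The exemption in section 6.1.5 sits in that visit. There is a small effect on reporting too: the SAP tabulates fertility status (section 6.1), and its Table 14.3.4.5.4 is limited to women of childbearing potential, so inconsistent classification changes who is counted.

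**Working it through.** The protocol gives no figure to reproduce here. The check sets the rules side by side and counts tests.

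**Step 1. Apply each rule to one woman:** high FSH at screening, less than 12 months of amenorrhea, none of the operations, no diagnosis of ovarian failure.

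| Source | Result |
|---|---|
| Criterion 16 | Of childbearing potential: 12 months without menses not reached |
| Section 6.3.4 | Not cleared: one FSH value does not suffice; investigate further |
| Sections 6.1.1, 6.1.4, 6.1.5, as worded | Exempt, if the FSH result is taken to show postmenopausal status |

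The first two rows agree and the third does not.

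**Step 2. Find where the exemption is written.** Inputs: sections 6.1.1 to 6.1.5, section 6.3.4 and Table 14-1 footnote h.

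| Visit | Test | Timing | Exemption in that visit's text? |
|---|---|---|---|
| Screening | Serum | Before infusion 1 | Yes (6.1.1) |
| Day 1 | Urine | Before infusion 1 | No (6.1.2) |
| Day 15 | Urine | Before infusion 2 | No (6.1.2) |
| Week 4 | Urine | After both | No (6.1.3) |
| Week 8 | Urine | After both | No (6.1.3) |
| Week 12 | Serum | After both | Yes (6.1.4) |
| Week 26 | Serum | After both | Yes (6.1.5) |

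**Step 3. Count.**

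- Scheduled tests: 3 serum + 4 urine = 7.
- Tests before an infusion: 1 serum + 2 urine = 3. Tests after both infusions: 7 − 3 = 4.
- Exemption applied only where it is written: she misses 3 and keeps 7 − 3 = 4. Of the 3 pre-infusion tests she misses 1, the only serum test before dosing. She keeps 3 − 1 = 2, one urine test before each infusion.
- Exemption taken to cover the whole study: she misses all 7, including all 3 before an infusion.
- Exemption read subject to section 6.3.4: her FSH does not show postmenopausal status, the exemption is not triggered, and she misses 0.

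The text therefore allows 0, 3 or 7 missed tests for the same woman, depending on how it is read.

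**The case against.** The strongest reply is that section 6.3.4 explains the exemption and does not compete with it. The visit sections do not speak of one high value. They require a test that shows postmenopausal status, and section 6.3.4 says what that status is and that one FSH value cannot establish it without 12 months of amenorrhea. Read together, the exemption would never reach the woman in question. This is a fair reading, and it may be what was intended. But the three exemption sentences refer to neither section 6.3.4 nor criterion 16, and they list FSH as a ground sufficient by itself. The reading would also leave ovarian failure as a ground for exemption that criterion 16 does not contain.

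The second reply concerns scope, and most of it stands. A reader might infer that such a woman can be dosed with none of the seven tests. The documents do not plainly provide for that. The exemption is written only at the three serum visits. The urine steps, including one before each infusion, still apply to any woman of childbearing potential, and criterion 16 says she is one. Four of the seven tests also come after the last infusion and cannot affect whether she is dosed. The broad reading remains possible because the exemption is from pregnancy testing in general, and the urine steps do not restate who counts as of childbearing potential. It is still only one reading.

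Two further inferences should not be drawn. The exemption does not change who must use contraception: criterion 16 sets that by its own definition. And the *and* joining the three operations in criterion 16, against *or* in the visit sections, is most likely loose drafting; requiring all three operations is not a realistic reading.

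**Conclusion.** The inconsistency is real and stands in the current protocol text. The exemption in sections 6.1.1, 6.1.4 and 6.1.5 lacks the amenorrhea condition that section 6.3.4 treats as necessary and on which criterion 16 rests. Applied as worded, it removes at least three of seven scheduled tests, including the only serum test before dosing, from a woman whom the protocol's own definition keeps in the monitored group. Only on the broad reading does it remove all seven.

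These counts assume that a site applies the visit-section wording without importing section 6.3.4. The documents do not give the number of women concerned, and it may be small: those with an FSH result taken as postmenopausal but less than 12 months of amenorrhea. No endpoint, analysis set or estimate is threatened. It should be corrected as a matter of participant protection and uniform conduct across sites.

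**What to change.** Reconcile the exemption sentences in sections 6.1.1, 6.1.4 and 6.1.5 with the note in section 6.3.4 and the definition in criterion 16 (section 4.1.2 and synopsis), so that one definition of childbearing potential decides who is tested. State whether the exemption also covers the urine tests in sections 6.1.2 and 6.1.3, and bring footnote h of Table 14-1 and its copy in SAP section 12.1 into line. The sponsor's clinicians must decide which rule stands, including on FSH and ovarian failure; none is proposed here.

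The cost is a wording change in a handful of places and, if the reconciled exemption is narrower, possibly a few more pregnancy tests.
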